10.2 Adverse Events

Adverse events (AEs) will be summarized and presented using primary MedDRA System Organ Classes (SOCs) and preferred terms (PTs) according to the version of the MedDRA coding dictionary used for the study at the time of database lock. The actual version of the MedDRA coding dictionary used will be noted in the AE tables and in the clinical study report. Specific adverse events will be counted once for each subject for calculating percentages, unless stated otherwise. In addition, if the same adverse event occurs multiple times within a subject, the highest severity and level of relationship to investigational product will be reported.

10.2.1 Treatment-Emergent Adverse Events

Treatment-emergent adverse events (TEAEs) are defined as any adverse events that begin or worsen in severity after initiation of upadacitinib during Study M16-046 or

[figure not shown]
Study M19-850 through 30 days following the last dose of upadacitinib. If an incomplete onset date is collected for an adverse event, the event will be assumed to be treatment-emergent unless there is other evidence that confirms that the event is not treatment-emergent (e.g., the event end date is prior to the study drug start date). Events where the onset date is the same as the study drug start date are assumed to be treatment-emergent. All treatment-emergent AEs in the Safety Population will be summarized during the administration of upadacitinib in Study M16-046 and/or Study M19-850, as well as by primary MedDRA SOC and Preferred Term. The SOCs will be presented in alphabetical order, and the PTs will be presented in alphabetical order within each SOC.

The number and percentage of subjects experiencing treatment-emergent AEs as well as exposure-adjusted number of events will be summarized.

10.2.2 Adverse Event Overview

An overview of TEAEs will be presented consisting of the number and percentage of subjects experiencing at least one event for each of the following TEAE categories:

- Any treatment-emergent AE
- Any treatment-emergent AE related to study drug according to the investigator
- Any severe treatment-emergent AE (Grade 3 and above according to NCI CTCAE version 5)
- Any serious treatment-emergent AE
- Any treatment-emergent AE leading to discontinuation of study drug
- Any treatment-emergent AE leading to death
 - All deaths will be summarized:
- Deaths occurring ≤ 30 days after last dose of study drug
- Deaths occurring > 30 days after last dose of study drug.

10.2.3 Treatment-Emergent Adverse Events by SOC and/or PT

Treatment-emergent adverse events will be summarized by SOC and PT; by maximum relationship to study drug as assessed by the investigator (e.g., reasonable possibility or no reasonable possibility) and SOC and PT; by SOC and PT and maximum toxicity; and by subject number and SOC and PT. Specific adverse events will be counted once for each subject for calculating percentages, unless stated otherwise. In addition, if the same adverse event occurs multiple times within a subject, the highest toxicity and level of relationship to investigational product will be reported.

In addition, treatment-emergent adverse events will be summarized by PT and sorted by decreasing frequency for the study treatment group.

The following summaries of adverse events will be generated:

- All TEAEs
- Treatment-emergent serious adverse events
- Treatment-emergent severe adverse events
- TEAEs related to study drug according to the investigator
- TEAEs leading to discontinuation of study drug
- TEAE leading to death

10.2.4 Treatment-Emergent Adverse Events per Patient-Years of Exposure

Exposure-adjusted number of TEAEs per 100 patient-years will be provided, where number of TEAEs per 100 patient-years of exposure are defined as the number of TEAEs divided by the total exposure in 100 patient-years. These will be presented for the following TEAE categories.

- Any TEAE
- Any treatment-emergent SAE
- Any TEAE leading to discontinuations of study drug

- Any severe TEAE
- Any TEAE related to study drug according to the investigator
- Any treatment-emergent SAE related to study drug according to the investigator
- Any TEAE leading to death

Note that one event per preferred term per day per subject will be counted in the calculation of the number of TEAEs (i.e., a preferred term will not be counted twice on the same day for the same subject). See the calculation method below:

• 100 * (Number of TEAEs)/(Total Patient Years)

where total patient years is defined as the sum of the study drug duration (defined in Section 6.0) + 1 days of all subjects normalized by 365.25, and rounded to 1 decimal place.

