Such an event can result from use of the drug as stipulated in the protocol or labeling, as well as from accidental or intentional overdose, drug abuse, or drug withdrawal. Any worsening of a pre-existing condition or illness is considered an AE. Worsening in severity of a reported AE should be reported as a new AE. Laboratory abnormalities and changes in vital signs are considered to be AEs only if they result in discontinuation from the study drug, necessitate therapeutic medical intervention, meets protocol specific criteria (see Section 6.2 regarding toxicity management) and/or if the investigator considers them to be AEs.

The investigators will monitor each subject for clinical and laboratory evidence of AEs at each visit throughout the study. All AEs will be followed to a satisfactory conclusion.

If any of the following events are reported, then the following supplemental report must be completed (Table 4).

Table 4. Supplemental Electronic Case Report Forms

Adverse Event	Supplemental Form
Cardiac events Myocardial infarction or unstable angina Heart failure Cerebral vascular accident and transient ischemic attack Venous thromboembolism	Cardiovascular (Cardiac) AE eCRF Myocardial Infarction and Unstable Angina AE eCRF Heart Failure Adverse Event eCRF Cerebral Vascular Accident and Transient Ischemic Attack AE eCRF Embolic and Thrombotic Event (Non-Cardiac, Noncentral nervous system [CNS]) eCRF
Herpes Zoster Infection	Herpes Zoster AE eCRF
ALT/AST > 3 ULN	Hepatic Abnormal Laboratory Value Supplemental eCRF Hepatic Supplemental Local Labs eCRF (if applicable) Hepatic Supplemental Procedure eCRF (if applicable)
Serum creatinine > 1.5 × the Baseline value and > ULN Serum creatinine ≥ 2.0 mg/dL	Renal Abnormal Laboratory Value Supplemental eCRF Renal Supplemental Local Labs eCRF (if applicable) Renal Supplemental Procedure eCRF (if applicable)
Creatine kinase (CPK) value ≥ 4 × ULN and no symptoms suggestive of myositis or rhabdomyolysis CPK ≥ 4 × ULN accompanied by symptoms suggestive of myositis or rhabdomyolysis CPK increases considered by the investigator to be an AE	Increased CPK Supplemental eCRF
Acne	Acne eCRF
Death	Death eCRF
Eczema herpeticum (or the synonymous Kaposi's varicelliform eruption)	Eczema herpeticum eCRF

AE = adverse event; ALT = alanine aminotransferase; AST = aspartate aminotransferase; CPK = creatine phosphokinase; eCRF = electronic case report form; ULN = upper limit of normal

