6.0 Study Drug Duration and Compliance

Study Drug Duration (in Days):

Summary of study drug duration and study drug compliance will be provided in M19-850 for the Safety Population during the entire treatment period. Study drug duration (days) will be summarized using the number of subjects, mean, standard deviation, minimum, median and maximum for each treatment group.

• Duration of upadacitinib is defined for each subject as last dose date of upadacitinib minus first dose date of upadacitinib +1,

[figure not shown]
In addition, the number and percentage of subjects exposed to upadacitinib will be summarized for the following categories of exposure duration for the Safety Population starting from the first dose of upadacitinib in M16-046 or M19-850:

- \bullet > 4 weeks
- ≥ 12 weeks
- \geq 24 weeks
- \geq 36 weeks
- \geq 48 weeks
- \geq 52 weeks
- \geq 64 weeks
- ≥ 76 weeks
- \geq 88 weeks
- ≥ 100 weeks
- ≥ 112 weeks
- \geq 124 weeks
- ≥ 136 weeks
- ≥ 148 weeks
- ≥ 160 weeks

Compliance:

Treatment compliance will be summarized in the Safety Population for the entire treatment period.

Upadacitinib compliance for an individual subject is defined as the number of upadacitinib actually taken (i.e., the difference between the number of tablets dispensed and the number of tablets returned) by the subject divided by the number of tablets planned to be taken by the subject during the study.

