10.2.6 Adverse Events of Special Interest

The AESI categories will be identified by the following search criteria per Standard MedDRA Queries (SMQs)/Company MedDRA Queries (CMQs) specified in Appendix B.

Overview and exposure-adjusted event rates per 100 patient-years of Treatment-emergent Adverse events of special interest will be provided.

Treatment-emergent Adverse events of special interest will be summarized by SOC and PT and listing format. Additionally, AESI rates per 100 patient years of study drug exposure using SOC by PT will be provided for each treatment group.

Information on the extent of herpes zoster infection and acne will be summarized as collected in the respective AE form.

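### AE and AESI rates per 100 patient-years count events for 30 days after last dose over on-drug time only, and have neither a first-event incidence rate nor a confidence interval

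*SAP*

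**What the plan says.** **Numerator.** Protocol 6.1 instructs sites: "Worsening in severity of a reported AE should be reported as a new AE". SAP 10.2.1 treats an event as treatment-emergent from the first upadacitinib dose "through 30 days following the last dose of upadacitinib". SAP 10.2.4 then applies one de-duplication rule: "one event per preferred term per day per subject will be counted in the calculation of the number of TEAEs".

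**Denominator.** SAP 6.0 defines duration as "last dose date of upadacitinib minus first dose date of upadacitinib +1". SAP 10.2.4 defines total patient-years from the "sum of the study drug duration (defined in Section 6.0) + 1 days of all subjects normalized by 365.25". The 30 days after last dose are not included.

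**Outputs.** SAP 10.2.6 says that "AESI rates per 100 patient years of study drug exposure using SOC by PT will be provided for each treatment group". SAP 10.2.1 and 10.2.2 also plan the number and percentage of subjects with events. Protocol 7.4 and SAP 10.2.1, 10.2.4 and 10.2.6 mention no confidence interval for any AE or AESI rate. Intervals at 95% are planned for efficacy means and percentages (SAP 9.1) and for mean changes in laboratory values and vital signs (SAP 10.3 and 10.4).

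**Follow-up.** Safety data start at the first upadacitinib dose in either study (SAP 10.1). Treatment lasts 52 weeks, with safety assessments continuing to Week 136 in ten listed countries and regions (SAP 2.2). The exposure categories in SAP 6.0 run to 160 weeks.

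**The concern.** TEAEs, SAEs, AESIs and AEs leading to discontinuation are primary endpoints (SAP 3.1), and the rates per 100 patient-years are their only exposure-adjusted summary. Three features limit that summary.

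- The numerator covers a longer period than the denominator, which pushes the rate upward.
- A worsening dated on a later day adds an event, so the figure is not a rate of distinct episodes.
- No interval is given. Protocol 7.3 rules out statistical testing, so an interval is the only way to show how much a low count can exclude.

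The percentages of subjects do not fill the gap. Upadacitinib-origin subjects bring up to 24 more weeks of exposure than dupilumab-origin subjects, and some countries follow subjects well beyond Week 52. A crude percentage mixes risk with length of observation. The plan therefore has a subject-level measure without exposure adjustment and an exposure-adjusted measure that is not subject-level.

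**Working it through.** The documents state no event count, patient-year total or rate, so there is no figure to reproduce. What follows applies the SAP formula.

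**1. Window mismatch.** Let D be the SAP 6.0 duration in days, which already includes its +1. The SAP denominator uses D + 1 and the numerator covers D + 30. With a constant event rate and a fully observed tail, the SAP rate divided by the matched-window rate is (D + 30)/(D + 1).

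| Exposure | D | Ratio | Excess |
|---|---|---|---|
| 52 weeks | 364 | 394/365 | 7.9% |
| 76 weeks (24 + 52) | 532 | 562/533 | 5.4% |
| 136 weeks | 952 | 982/953 | 3.0% |
| 160 weeks (24 + 136) | 1,120 | 1,150/1,121 | 2.6% |

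Sensitivity of these figures:

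- *Early stopping (assumption).* If 10% to 30% stop uniformly over 52 weeks, mean exposure is 345.8 to 309.4 days and the excess is 8.4% to 9.3%.
- *Prior exposure (assumption).* If half the subjects bring 24 weeks from M16-046 and all complete 52 weeks, mean D is 448 and the excess is 478/449 − 1 = 6.5%. The allocation in M16-046 is not given in these documents.
- *Rarer post-dose events (assumption).* At half the on-drug rate, the excess at 52 weeks is about 15/364 = 4.1%, before the surplus day.
- *Still on drug at the interim.* These subjects have no tail, so no excess.
- *Second +1.* At 52 weeks it multiplies the rate by 364/365, a fall of 0.3%.

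**2. Worsenings.** An episode recorded at Grades 1, 2 and 3 on three different days gives three events in the any-TEAE row. If a share w of records are worsenings of an episode already counted, the excess over episodes is 1/(1 − w) − 1. This is 2.0%, 5.3%, 11.1% and 25.0% for w = 2%, 5%, 10% and 20%. The documents give no value for w, so these are illustrations only.

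**3. Precision.** With 600 subjects at 52 weeks each (assumption), the SAP formula gives 600 × 365/365.25 = 599.6 patient-years. Adding the tail instead of the surplus day gives 600 × 394/365.25 = 647.2. Ten events are then 1.67 per 100 patient-years under the SAP and 1.55 with matched windows. Exact Poisson 95% limits at 599.6 patient-years, treating events as independent, are:

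| Events | Rate per 100 PY | 95% limits |
|---|---|---|
| 0 | 0.00 | 0 to 0.62 |
| 3 | 0.50 | 0.10 to 1.46 |
| 10 | 1.67 | 0.80 to 3.07 |

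If half the subjects bring 24 earlier weeks, exposure is (300 × 532 + 300 × 364)/365.25 = 736 patient-years. The zero-event upper limit is then 100 × 3.689/736 = 0.50, where 3.689 = −ln 0.025.

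**The case against.** The strongest defence is that SAP 10.2.4 openly defines a number of events per 100 patient-years and states its counting rule. The measure misleads only someone who reads it as incidence or as distinct episodes. That stands, and it limits the point. Several stronger readings that a reader might infer are not supported:

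- *That many affected subjects cannot be told from a few with repeated records.* Numbers and percentages of subjects appear beside the event rates, each subject is counted once for percentages (SAP 10.2 and 10.2.3), and SAP 10.2.7 lists subject numbers by preferred term.
- *That every rate is inflated by worsenings.* In the severe row, the Grade 1 to 3 episode gives one event. Earlier non-serious records do not enter the SAE row, and a death occurs once.
- *That laboratory-type AESIs are the most exposed.* Protocol 6.1 makes a laboratory abnormality an AE only under stated conditions, and nothing shows how often such records worsen.
- *That no primary safety endpoint has a measure of precision.* Laboratory and vital-sign mean changes have 95% intervals.
- *That the window mismatch is large.* A subject who stops at 8 weeks has an excess of 86/57 − 1 = 51%, but that is one subject, not a pooled rate.

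The defence does not remove the mismatch, the missing intervals or the lack of an exposure-adjusted subject-level rate. The percentages answer who was affected, but not over how much time.

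**Conclusion.** The point holds as a modest defect with an inexpensive remedy. It does not show that the primary safety rates are seriously misstated.

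The window mismatch overstates event rates by about 3% to 8% for subjects with 52 to 136 weeks of exposure, given a constant event rate and a fully observed tail. It is somewhat more with early stopping and less if post-dose events are rarer or incompletely captured. The second +1 is negligible. Later-dated worsenings mean that the rate is not one of distinct episodes, by an amount that the documents do not allow anyone to derive.

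The more useful finding is what is absent: an exposure-adjusted incidence rate, and an interval on any AE or AESI rate. Without an interval, a reported zero does not show that about 0.5 to 0.6 per 100 patient-years remains compatible with the data, on an assumed 736 to 600 patient-years.

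**What to change.** In SAP 10.2.4 and 10.2.6:

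- For SAEs, deaths, AEs leading to discontinuation and each AESI, add the exposure-adjusted incidence rate, overall and by M16-046 group. This is the number of subjects with at least one event divided by total person-time. Person-time runs to the first event or, if there is none, to the earliest of last dose + 30 days, last contact and data cutoff.
- Give it an exact Poisson 95% interval. Each subject contributes at most one event, so the interval is not undermined by repeat records, as a simple Poisson interval on the event rate would be.
- Keep the current event rate as supportive and drop the second +1. Add a footnote that it counts worsenings as events and sets events up to 30 days after last dose over on-drug exposure.
- Collapsing records created only by a severity change is optional. The documents do not show that the eCRF links them, so it may take extra work.

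The cost is SAP wording and extra table columns from data already collected, with no change to study conduct. The downside is a second rate to explain.

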10.2.5 SAEs (Including Deaths) and Adverse Events Leading to Study Drug Discontinuation

[figure not shown]
SAEs (including deaths) and AEs leading to study drug discontinuation will be summarized by SOC and PT and in listing format.

10.2.6 Adverse Events of Special Interest

The AESI categories will be identified by the following search criteria per Standard MedDRA Queries (SMQs)/Company MedDRA Queries (CMQs) specified in Appendix B.

Overview and exposure-adjusted event rates per 100 patient-years of Treatment-emergent Adverse events of special interest will be provided.

Treatment-emergent Adverse events of special interest will be summarized by SOC and PT and listing format. Additionally, AESI rates per 100 patient years of study drug exposure using SOC by PT will be provided for each treatment group.

Information on the extent of herpes zoster infection and acne will be summarized as collected in the respective AE form.

10.2.7 Listing of Adverse Events

The following additional summaries will be provided for treatment-emergent adverse events, unless otherwise specified.

- List of subject numbers associated with each PT for TEAEs.
- List of subject numbers associated with each PT for TEAEs related to study drug according to the investigator
- Listing of treatment-emergent SAEs.
- Listing of TEAEs leading to discontinuation of study drug.
- Listing of all deaths.
- Listing of treatment-emergent AESIs.

10.2.8 Acne Adverse Events

The investigator-identified acne AEs will be summarized by involvement, morphology, and predisposing factors.

10.3 Analysis of Laboratory Data

Data collected from central and local laboratories, including additional laboratory testing due to an SAE, will be used in all analyses, except for Baseline where SAE-related laboratory assessments on or before the first dose of study drug will be excluded. For the assessments of laboratory data, values collected more than 30 days after the last dose of study drug will be excluded. The clinical laboratory tests defined in the protocol operations manual (e.g., hematology and clinical chemistry) will be summarized.

Table 1. List of Laboratory Variables

[figure not shown]
Clinical Laboratory Tests								
Hematology	Clinical Chemistry	Other Tests						
Hematocrit Hemoglobin RBC count WBC count Neutrophils Bands Lymphocytes Monocytes Basophils Eosinophils	BUN Creatinine Total bilirubin INR (reflex only) ^a Albumin ALT AST Alkaline phosphatase CPK Sodium	Central Lab Tests: Serum pregnancy (beta human chorionic gonadotropin [bHCG]) test Hepatitis B virus deoxyribonucleic acid polymerase chain reaction (HBV DNA PCR [Per Toxicity Management Guidelines only]) QuantiFERON-TB Gold High-sensitivity C-reactive protein (hsCRP) Local Lab Tests: Urine pregnancy test						
Platelet count Urinalysis Specific gravity Ketones pH Protein Blood Glucose Urobilinogen Bilirubin Leukocytes Nitrites Microscopic examination, if needed Potassium Bicarbonate/CO2 Chloride Calcium Inorganic phosphoru Uric acid Total protein Glucose Cholesterol LDL-C Triglycerides		PPD test/T-SPOT TB						

ALT = alanine aminotransferase; AST = aspartate aminotransferase; BUN = blood urea nitrogen; CO² = carbon dioxide; CPK = creatine phosphokinase; DNA = deoxyribonucleic acid; HBV = hepatitis B virus; HDL-C = high-density lipoprotein cholesterol; INR = international normalized ratio; LDL-C = low-density lipoprotein cholesterol; PCR = polymerase chain reaction; PPD = purified protein derivative (tuberculin); RBC = red blood cell; TB = tuberculosis; WBC = white blood cell

Each laboratory variable will be summarized for the following time points:

• Subjects originally randomized to dupilumab in Study M16-046 and continued in Study M19-850: All post-baseline visits in M19-850. The Baseline for this group is defined as the last non-missing observation on or before their first dose of study drug in M19-850.

a. INR will only be measured if ALT and/or AST $> 3 \times$ upper limit of normal (ULN).

• Subjects originally randomized to upadacitinib in Study M16-046 and continued in Study M19-850: All post-baseline visits in M16-046 and M19-850. The Baseline for this group is defined as the last non-missing observation on or before their first dose of study drug in M16-046.

The summary includes the number of non-missing observations, mean and standard deviation, median, minimum and maximum. Mean change from baseline to each applicable post-baseline visit mentioned above will be summarized for selected laboratory variables, with the number of observations, baseline mean, and visit mean. The change from baseline mean, standard error, and 95% confidence interval will be presented for the mean change from baseline.

Changes in laboratory parameters will be tabulated using shift tables by NCI CTC criteria version 4.03. A shift table from baseline either to the worse value (based on NCI CTC criteria) during treatment or to minimum and maximum value (based on normal range), will be created. A similar shift table will be provided to summarize shifts from baseline to the final post-baseline value.

Laboratory abnormalities meeting CTC criteria grade 3 and 4 will be summarized.

Laboratory abnormalities will be evaluated based on Potentially Clinically Important (PCI) criteria during the administration of upadacitinib in Study M16-046 and Study M19-850 (Appendix C). For each laboratory PCI criterion, the number and percentage of subjects who have a laboratory value meeting the criteria will be summarized. Listings will be provided to summarize subject-level laboratory data for subjects meeting PCI criteria.

According to FDA's Guidance for Industry Drug-Induced Liver Injury: Premarketing clinical evaluation (July 2009), when aminotransferase (AT) abnormalities indicating hepatocellular injury are accompanied by evidence of impaired hepatic function (bilirubin elevation > 2 × ULN), in the absence of evidence of biliary obstruction (i.e., significant elevation of ALP) or some other explanation of the injury (e.g., viral hepatitis, alcohol

hepatitis), the combined finding (i.e., Hy's Law cases) represents a signal of a potential for the drug to cause severe DILI. For the purpose of assessing for potential Hy's law cases, the frequencies and percentages of subjects with post baseline liver specific function test values that meet the following criteria of potential clinical interest should be presented:

- ALT \geq 3 × ULN
- ALT \geq 5 × ULN
- ALT $\geq 10 \times ULN$
- ALT $\geq 20 \times ULN$
- AST \geq 3 × ULN
- AST \geq 5 × ULN
- AST $\geq 10 \times ULN$
- AST $\geq 20 \times ULN$
- TBL $\geq 2 \times ULN$
- Alkaline phosphatase $\geq 1.5 \times ULN$
- ALT and/or AST \geq 3 × ULN and concurrent TBL \geq 1.5 × ULN
- ALT and/or AST \geq 3 × ULN and concurrent TBL \geq 2 × ULN

